7 STUDY POPULATION

7.1 Study Subject Recruitment and Selection

This study will enroll up to 725 male or female subjects, between the ages of ≥ 18 months of age and < 72 months of age from multiple recruitment sites.

Subjects may also be recruited from the Investigator's existing patient database or from patients who present themselves to the study site requesting evaluation.

Only subjects who meet all eligibility criteria and who provide informed consent will be enrolled into the study.

Each subject will be evaluated by the primary HCP to assess his/her suitability for entry into the study according to the following inclusion and exclusion criteria.

7.2 Inclusion Criteria

To be included in the study, subjects must meet all of the following Inclusion Criteria:

- Caregiver must be able to read, understand and sign the Informed Consent Form (ICF).
- Caregiver or HCP concern for developmental delay.
- Female or Male, ≥ 18 to <72 months of age.
- Functional English capability in the home environment.
- Caregiver must have smartphone capabilities for downloading the Cognoa Research App (Cognoa supports iOS 10.0 and up, Android 6.0 and up).
- Participants must be willing to be videotaped during the diagnostic assessment by the specialist clinician.

7.3 Exclusion Criteria

Subjects will be excluded from the study if they meet any of the following Exclusion Criteria:

- Subjects with a prior diagnosis of ASD rendered by a healthcare professional.
- Subjects with suspected auditory or visual hallucinations or with prior diagnosis of childhood onset schizophrenia.
- Subjects with deafness or blindness.
- Subjects with known physical impairments affecting their ability to use their hands.
- Subjects with major dysmorphic features or prenatal exposure to teratogens (such as fetal alcohol syndrome).
- Subjects with history, suspicion, or diagnosis of genetic conditions (such as Rett's Syndrome or Fragile X).
- Subjects with microcephaly.
- Subjects with history or prior diagnosis of epilepsy or seizures.
- Subjects with a history of neglect.
- Subjects with a history of brain malformation, injury or insult requiring interventions such as surgery or chronic medication.
- Subjects whose age on the date of enrollment is outside the target age range.
- Subjects or caregivers who have been previously enrolled in any Cognoa clinical study or survey.
- Subjects whose medical records had been included in any internal Cognoa training or validation sets.

7.4 Subject Number

If a caregiver completes the Informed Consent Form, meets the study eligibility criteria and is willing to participate, the subject will be assigned a study subject identification number.

This subject identification number will have no relation to Personally Identifiable Information (PII, defined as any data that could potentially identify a specific individual), such as date of birth, initials, medical record number, etc. All data transmitted and used for analysis will be identified by ID number and not subject identifying information.

7.5 Subject Discontinuation Criteria

If possible, every subject should remain in the study until completion of the required follow-up period. However, participation in this study is completely voluntary and a subject can choose to withdraw from the study at any time. Decision to withdraw will not affect or prejudice the subject's continued medical care in any way. In those instances, the investigator will attempt to obtain a final clinical assessment and an adverse device effect evaluation for the subject prior to this withdrawal. A subject will be considered lost to follow-up only after three unsuccessful, documented attempts to contact the subject have been made.

In addition, a subject can be discontinued for any of the following reasons: the Principal Investigator decides that continuing in the study would not be in the subject's best interest, a subject is noncompliant with the protocol, a subject has a serious reaction to the treatment, a subject develops any of the exclusion criteria during the study period or the study is stopped by the study sponsor.

8 DATA COLLECTION AND STORAGE

To maintain confidentiality, subjects will be assigned a unique subject ID number (see section 7.4 subject number), which will be used on all case report forms and linked to the Informed Consent Forms for audit and verification purposes. All data transmitted and used for analysis will be identified by ID number rather than subject-identifying information.

Authorized representatives of institutions participating in the study, the Food and Drug Administration (FDA), the Sponsor, and the reviewing IRB and other groups or organizations that have a role in this study will have access to and may view a subject's study information. They will be subject to regulations protecting patient confidentiality (e.g., HIPAA).

Data collection will be completed using electronic and/or paper report forms provided by the Sponsor, and data will be recorded into the Sponsor dedicated study data repository.

Data repository will include:

- Demographic information (child age, child biological sex, child race, child ethnicity, caregiver level of education)
- Device Inputs
 - Caregiver assessment
 - Video analysis
 - Primary HCP assessment
- Device Output
- Diagnostic assessment for ASD according to DSM-5 diagnostic criteria, by the diagnosing specialist clinician
- Medical, Developmental history and Physical
- Diagnostic review outcome of reviewing specialist clinicians

The data will be stored securely on an Amazon S3 cloud server with secured access and SSL encryption. Any data collected on paper will be kept in a secure and locked location at the primary HCP's or specialist clinician's office and periodically transferred to a central research coordinator at each site, before being recorded in an electronic format by the study staff and stored on a HIPAA-secure server.

All data will be retained for at least 7 years from the completion of the Study. Data collected on paper may be retained solely in electronic format.

9 ADVERSE EVENTS AND ADVERSE DEVICE EVENTS

9.1 Definitions

9.1.1 Adverse Event (AE)

An adverse event (AE) is defined as any untoward medical occurrence, unintended disease or injury, or untoward clinical signs (including abnormal laboratory findings) in subjects, device users or other persons, whether or not it is related to the investigational medical device. Expected Adverse Device Events (ADEs) may be previously identified in nature, incidence, severity or outcome in the study protocol, informed consent document, device operator manual, other risk analysis documentation or regulatory application.

9.1.2 Serious Adverse Event (SAE)

A serious adverse event (SAE) is any adverse event, whether related to the use of an investigational device or clinical study device, that:

- led to a death;
- led to a serious deterioration in the health of the subject that:
 - resulted in a life-threatening illness or injury;
 - resulted in a permanent impairment of a body structure or body function;
 - required in-patient hospitalization or prolongation of existing hospitalization;

- resulted in medical or surgical intervention to prevent permanent impairment to a body structure or a body function;
- led to fetal distress, fetal death or a congenital abnormality or birth defect.

9.1.3 Anticipated Serious Adverse Device Effect (ASADE)

[figure not shown]
An anticipated serious adverse device effect (ASADE) is any SAE on health or safety or any life-threatening problem or death caused by, or associated with the device, if that effect, problem, or death was previously identified in nature, severity, or degree of incidence in the investigational plan, informed consent, operator manual, other risk analysis documentation or regulatory application; or any other serious problem associated with a device that relates to the rights, safety, or welfare of subjects.

9.1.4 Unanticipated Serious Adverse Device Effect (USADE)

An unanticipated serious adverse device effect (USADE) is any SAE on health or safety or any life-threatening problem or death caused by, or associated with the device, if that effect, problem, or death was not previously identified in nature, severity, or degree of incidence in the investigational plan, informed consent, operator manual, other risk analysis documentation, or regulatory application; or any other unanticipated serious problem associated with a device that relates to the rights, safety, or welfare of subjects.

In subjects, the ADEs/SADEs include the effects related to the investigational medical device (clinical study device), or the procedures involved. For device users or other persons (other clinical staff in the treatment room) ADE/SADE is restricted to the effects related to investigational medical devices. ADEs/SADEs may include the effects (1) resulting from insufficient or inadequate instructions for use, deployment, installation, or operation, or any malfunction of the investigational medical device; or (2) resulting from user error or from intentional misuse of the investigational medical device.

Figure 1. Flowchart for classification of adverse device events

9.2 Recording AEs/ADEs and SAEs/SADEs

All AEs/SAEs or ADEs/SADEs will be: (1) evaluated and must be recorded in the subject's study case report forms (CRFs); (2) monitored and tracked from the time of the first treatment.

At each contact with the subject, the investigator must seek information on AEs/ADEs/SADEs by specific questioning and, as appropriate, by examination. AEs/ADEs/SADEs may be observed by the investigator and/or clinical research staff, elicited from the subject and/or family member or volunteered by the subject. All observed and volunteered adverse signs and symptoms, anticipated or unanticipated, regardless of severity or frequency, will be recorded in the case histories (medical chart and CRFs). Included in the description should be the nature of the sign or symptom, the date of onset, date of resolution (duration), the severity, anticipated or unanticipated, the relationship to study treatment or other therapy, the action taken (if any), and the outcome.

All SAEs/SADEs, anticipated or unanticipated, must be reported to Cognoa immediately but not later than 5 working days. The SADE must be recorded in: (1) the CRF and (2) a written report must be submitted to Cognoa within five (5) working days after the investigator first learns of the event and is to include a full description of the event and sequelae, in the format detailed by the Cognoa Serious Adverse Event Form.

9.3 Follow-up of Subjects after AEs

All reported AEs/ADEs/SAEs/SADEs should be followed until resolution or until the subject's participation in the study ends. Resolutions of AEs/ADEs/SAEs/SADEs are to be documented on the appropriate CRFs. All ADEs that result in permanent discontinuation from this clinical trial, whether serious or not, should also be reported on the subject Non-Completion of Study Form.

10 POTENTIAL RISKS / BENEFITS

10.1 Potential Risks

Risks related to the study are expected to be minimal.

There are no physical risks of participating in the study. However, one risk could be psychological. Caregivers may feel some discomfort in answering questions about their child's behavior. Children might also feel some discomfort being filmed for the video analysis.

Another potential risk is the possible release of sensitive medical, behavioral, or educational information. To mitigate the risk of releasing sensitive personal information, we adhere to confidentiality protocols to protect the privacy of personal information. When data is published, it is always anonymous and in a manner so that specific families or subjects cannot be identified.

10.2 Potential Benefits

The subjects may or may not benefit from the study.

Potential benefit is to identify subjects with ASD, thus enabling earlier therapy, which is known to positively impact long-term outcomes. All subjects in the study will receive an appointment with a specialist clinician, which is likely to occur in an expedited manner relative to their referral path were they not participating in the clinical study.

11 DATA ANALYSIS PLAN

11.1 Sample Size

This is a multi-site, prospective, blinded, active comparator study with up to 725 subjects who have been deemed appropriate for evaluation of the device.

11.2 Analysis Sets

The analysis set will include all enrolled subjects who complete assessment.

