4 STUDY ENDPOINTS

4.1 Effectiveness endpoints

The primary endpoints of this study are:

- (1) to achieve a composite of positive predictive value (PPV) greater than 65% and negative predictive value (NPV) greater than 85% for the device in relation to the clinical reference standard in the overall study population, and
- (2) measurement of the proportion of all children for whom the Device provides no result.

The secondary endpoints are:

- (1) sensitivity of the device in relation to the clinical reference standard in the overall study population and
- (2) specificity of the device in relation to the clinical reference standard in the overall study population.

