The video analysts will not have access to the caregiver assessment or the primary HCP assessment. If the videos are not scoreable (e.g., if one or more videos are unhelpful for any reason such as: poor lighting, poor video or audio quality, bad vantage point, child not present or identifiable within a group, insufficient interaction with the child), the caregiver will be asked to submit additional videos. Caregivers will be allowed a maximum of 60 days from submitting the caregiver assessment (Module 1) to complete video upload or provide scoreable videos. Caregivers will be given guidance points on how to record videos.

Either during the primary care appointment when the patient was informed about the study or in a timely manner after the appointment, the primary care physician will answer the primary HCP assessment about the child's behavior and development. The clinician will only answer the assessment if the caregiver provides an initial consent. If the caregiver chooses not to participate in the study, the primary HCP assessment will be securely destroyed. The HCP will not have access to the responses in the caregiver assessment (Module 1), the patient videos, or the video's analysis (Module 2).

Once the caregiver assessment, primary HCP assessment, and scored videos have been submitted, the device will generate a diagnostic output. The device output will be recorded by Sponsor in a dedicated study data repository.

It will not be shared with the referring HCP, caregivers, or specialist clinicians performing diagnosis and review.

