2.2 Primary Endpoints

1. Composite endpoint consisting of:
 - a. Positive Predictive Value (PPV) of the device, greater than 65%
 - b. Negative Predictive Value (NPV) of the device, greater than 85%

2. Proportion of all subjects receiving "no result" output

The first, composite primary endpoint will be evaluated for success or failure as a group. For sample size and power analysis purposes, the overall error rate is controlled on a per-endpoint basis. For full specifications of the analysis of the primary endpoints, refer to section 5.1 *Analysis Methods* of this document. For full sample size calculations, refer to section 5.5 *Sample Size and Power Analysis* of this document.

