2.6 Mitigation of Bias

2.6.1 Verification bias:

No verification bias is expected to be present. All study participants will receive the reference standard diagnosis and be assessed by the device.

2.6.2 Selection bias:

No selection bias is expected to be present. The study enrollment criteria are set to match the intended indications for use of the device. Specifically, the parental level of concern for possible autism confirmed by the HCP and allowed age range are managed. For more details, refer to section *IV. Study Subjects of the Protocol*.

2.6.3 Spectrum bias:

No spectrum bias is expected to be present. The study design adopts open enrollment that is expected to enroll children from these relevant subgroups at the rates at which they are present in the target population:

- Children who are developing normally
- Children with ASD
- Children with other neurodevelopmental conditions such as ADHD, speech and language delay, etc.
- Children with both ASD and one or more other neurodevelopmental conditions

The proportions of children in the sample with these conditions are expected to match the proportions of children in the target population with these conditions, and the observed proportions will be reported.

2.6.4 Training bias:

No training bias is expected to be present. Every caregiver will undergo the device assessment only once, and all previous Cognoa users are excluded from the study. Therefore, no individual user will have the opportunity to change their ability with the device over the course of the study. Health Care Provider (HCP) users will be trained on using the device prior to the commencement of the study, in order to reduce the risk that a HCP changes how they use the device over the course of the study.

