4.2 Analysis Populations

The analysis will be performed on an intention-to-diagnose basis [2]. The analysis population will include all participants. For details on how dropouts, missing data, and protocol noncompliance will be analyzed, refer to section 5.2 *Handling of Dropouts and Missing Data* of this document.

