5.1 Analysis Methods

5.1.1 Analysis of the Primary Endpoints

The Predictive Values of the device outcomes will be computed as:

Device Outcome	Probability of Interest	Computation	Minimally Acceptable Value
+ASD	$PPV = P(\text{Ref}=\text{+ASD} \text{Device}=\text{+ASD})$	$\frac{TP}{TP + FP}$	0.65
-ASD	$NPV = P(\text{Ref}=\text{-ASD} \text{Device}=\text{-ASD})$	$\frac{TN}{TN + FN}$	0.85

Two-sided 95% confidence intervals of each metric will be computed and reported. If both confidence intervals lie entirely above the minimally acceptable values, the endpoint will be considered to be met.

The proportion of all subjects who receive a "no result" outcome will be computed as:

Device Outcome	Probability of Interest	Computation
no result	$P(\text{Device}=\text{no result})$	$\frac{NRP + NRN}{\Sigma all}$

A two-sided 95% confidence interval around the metric will be computed and reported.

Note that the values used in the computation of the metrics used in the analysis of the primary endpoints are only defined for data-complete subjects. Therefore, in the analysis of the primary endpoints only subjects who complete the device assessment will be included. Additional analyses will be performed on subjects who drop out, as specified in section 5.2 *Handling of Dropouts and Missing Data* of this document.

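### The completer-only analysis set can leave children whose submitted videos stay unscoreable out of the no-result primary endpoint, which may understate how often the device gives no answer.

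*Protocol*

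**What the plan says.** **Definition of the endpoint.** Protocol 4.1 gives the second primary endpoint as "measurement of the proportion of all children for whom the Device provides no result". SAP 2.2 begins its version with "Proportion of all subjects receiving" and goes on to name a no-result output. SAP 4.2 labels the analysis intention-to-diagnose and adds "The analysis population will include all participants".

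**Who is analysed.** Protocol 11.2 states "The analysis set will include all enrolled subjects who complete assessment". SAP 5.1.1 states that "in the analysis of the primary endpoints only subjects who complete the device assessment will be included". It computes the no-result proportion as (NRP + NRN) over all subjects. In the SAP section 5 table, NRP and NRN are no-result children classified by the reference diagnosis.

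**How an output arises.** Protocol section 6 states "Once the caregiver assessment, primary HCP assessment, and scored videos have been submitted, the device will generate a diagnostic output". If videos cannot be scored, the caregiver is asked for more, with a limit of 60 days from submission of the caregiver assessment. The research coordinator's call to book the specialist visit follows submission of scorable videos.

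**Missing data.** SAP 5.1.1 promises that "Additional analyses will be performed on subjects who drop out" and points to SAP 5.2. That section keeps non-completers in the records and reports them. Its imputation covers a missing reference diagnosis only. SAP 2.6.1 assumes the problem away: "All study participants will receive the reference standard diagnosis and be assessed by the device".

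**The concern.** The endpoint tells a provider how often the device will give no answer. There are two ways for that to happen. The algorithm can abstain on complete inputs, or the inputs can fail, because the videos supplied cannot be scored. Protocol section 2 makes the caregiver app, the Video Analyst Portal and the video module parts of the device. SAP section 5 ties the no-result category to a sample that cannot be evaluated. An unscoreable video fits that description.

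Followed literally, SAP 5.1.1 counts only the first kind of failure, while the endpoint's definition and the intention-to-diagnose label suggest that everyone is counted. A reader of the result could take an abstention rate among successfully processed children for the overall rate of no answer. The glossary describes a dropout as someone who discontinues participation. A caregiver who kept sending videos that were rejected has not clearly done that, so the general reference to dropouts does not settle where these children belong.

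**Working it through.** **Step 1. Follow one child.** The caregiver assessment is in, videos have been submitted, and none is scoreable at day 60.

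- Device output: none, because Protocol section 6 makes scored videos a condition of output.
- Specialist visit: not triggered under the Study Flow, so no reference diagnosis is planned.
- SAP section 5 table: no cell fits. The three device rows need an output and the two columns need a reference diagnosis.
- SAP 5.1.1: excluded, because the device assessment is not complete.
- SAP 5.2: reported as a non-completer. Its imputation rule works from an existing device response, and there is none.

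So the child is disclosed but does not enter the endpoint.

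**Step 2. Reproduce the plan's figures (SAP 5.4).**

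- Completers: 725 × (1 − 0.25) = 543.75, so 544. Non-completers: 725 − 544 = 181. (The text of SAP 5.4 also gives 525; its table uses 544, and so does this check.)
- Expected no-result children: 0.31 × 544 = 168.6, so 169.
- Proportion: 169/544 = 31.07%, exact (Clopper-Pearson) 95% CI 27.20% to 35.14%.
- Normal-approximation half-width: 1.96 × √(0.31 × 0.69/544) = 3.9 percentage points, inside the SAP's stated ±7.5%.

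The figures reproduce, and they show that the planned denominator is the 544 completers.

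**Step 3. Add u children with submitted but unscoreable videos to numerator and denominator.** The inclusive proportion is (169 + u)/(544 + u). Its excess over 169/544 is 375u/[544 × (544 + u)], which is never negative. The documents do not give u, so every value below is an assumption.

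| u | Share of 181 | Inclusive proportion | Exact 95% CI |
|---|---|---|---|
| 0 | 0% | 169/544 = 31.1% | 27.2 to 35.1% |
| 9 | 5% | 178/553 = 32.2% | 28.3 to 36.3% |
| 18 | 10% | 187/562 = 33.3% | 29.4 to 37.3% |
| 45 | 25% | 214/589 = 36.3% | 32.4 to 40.4% |
| 181 | 100% | 350/725 = 48.3% | 44.6 to 52.0% |

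The estimate first passes the completers' upper limit of 35.14% at u = 35 (204/579 = 35.23%). The last row is an arithmetical ceiling only: it would make every planned dropout a video failure.

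**Step 4. Count children with an output but no specialist visit.** A no-result proportion needs no reference diagnosis, so these children belong in it. Suppose there are 100, abstaining at 31% (assumed). The abstention proportion is (169 + 31)/(544 + 100) = 200/644 = 31.1%. With u = 18 the inclusive proportion is 218/662 = 32.9%, so the gap narrows from 2.2 to 1.9 points.

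**Step 5. Test a wider denominator.** Suppose everyone with a caregiver assessment were in the denominator, including 20 children (assumed) who lack an output for other reasons. Then u = 5 gives 174/569 = 30.6%, below the present 31.1%, and u = 9 gives 178/573 = 31.1%, no change. That denominator can hide what it is meant to show.

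**The case against.** The best defence is that the SAP means abstention and nothing else. SAP 2.2 speaks of an output that is received, section 5 describes an option the device has to abstain, and SAP 5.4 takes its 169 from study completers. The listed reasons for unscoreable video, such as lighting, vantage point or an absent child, are mainly recording problems, and resubmission is allowed. SAP 5.1.1 states its restriction openly and gives a reason: the cell counts are defined only for data-complete subjects. All of this is fair, and it means the plan has a tenable narrow reading. It does not remove the wider one. Protocol 4.1 speaks of the device providing no result, and SAP section 5 refers to samples that cannot be evaluated. The plan does not choose between them.

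A second objection is that the missing reference diagnosis is inferred. Protocol 10.2 promises every subject a specialist appointment, and the Randomization entries in the Protocol Summary and section 6 say all subjects will be scheduled for both assessments. That stands: no sentence says what happens after day 60, and the scheduling trigger is only the more specific text. Even with a specialist visit, though, the child has no device output and still fails the SAP 5.1.1 rule.

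Third, the meaning of intention-to-diagnose rests on a cited source that is not in the documents. Only the commitment to include all participants can be held against the plan.

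Fourth, a reader might infer that every child without scoreable videos at day 60 is a device failure. The text does not support that. The 60-day limit also covers families who never completed an upload, and they may simply have disengaged.

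**Conclusion.** The point holds as an inconsistency between the endpoint's definition and its analysis set. Children with submitted but unscoreable videos have no assigned place in a primary endpoint whose wording could cover them. With everything else held fixed, leaving them out lowers the no-result proportion or leaves it unchanged.

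The size is unknown. Under the SAP's planning figures it is 0 points if u = 0, 2.2 points if u = 18 and 5.3 points if u = 45. Those values of u are illustrations; the only anchor is an all-cause dropout rate of up to 25%.

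A reader might infer that the true no-result rate is near 48%, or that the trial's success criterion is compromised. Neither follows. The first needs every dropout to be a video failure. On the second, this endpoint has no performance goal, and PPV and NPV use only positive and negative outputs. Nor do the documents show that the narrow reading is wrong. They show that two readings are open and that the choice should be made before the data are seen. This is worth correcting, at moderate priority.

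**What to change.** 1. In SAP 5.1.1 and Protocol 11.2, limit the need for a reference diagnosis to PPV and NPV.
2. For endpoint 2, compute the abstention proportion among all children with complete device inputs, whether or not a reference diagnosis exists.
3. Beside it, report an inclusive no-result proportion. It adds to both numerator and denominator the children who submitted videos but had none scoreable at 60 days.
4. Show never-uploaded videos, missing HCP assessments and withdrawals in separate rows of a participant-flow table, outside both the numerator and the denominator of the inclusive proportion.
5. State this handling of a missing device output in SAP 5.2 before unblinding.

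**Cost.** The wording changes need a signed amendment and IRB approval before implementation (Protocol 12.5). Enrolment was already at 600, with 217 specialist visits completed, when the SAP was revised. That revision records that the sponsor had no insight into results, and SAP 2.1 keeps the blind until the study ends, so the choice can still be made blind. Protocol section 8 lists the video analysis among stored inputs but no scoring-failure status, so a small extra tabulation of video status at 60 days is needed. The sponsor may have to report a higher no-result figure. PPV, NPV and the success rule stay as they are.
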